8.0 Statistical Methods and Determination of Sample Size

8.1 Statistical and Analytical Plans

The primary analysis will occur after all subjects have completed the PT Week 12 Visit or prematurely discontinued treatment. The data for the primary analysis will be locked after data cleaning. Data after PT Week 12 will be added to a new version of the database which will be cleaned and locked at the end of the study.

SAS[®] (SAS Institute, Inc., Cary, NC) for the UNIX operating system will be used for all analyses. All confidence intervals will be two-sided with an alpha level of 0.05.

Descriptive statistics will be provided, such as the number of observations (N), mean, and standard deviation (SD) for continuous variables and counts and percentages for discrete variables.

Safety, and demographic analyses will be performed on all subjects who receive at least one dose of study drug.

Efficacy analyses will be performed on the intention-to-treat (ITT) population defined as all enrolled subjects who receive at least one dose of study drug, unless otherwise specified.

Sensitivity analyses of the primary efficacy endpoint, when applicable, will be performed on the intention-to-treat population modified to exclude subjects not of GT5, 6 according to phylogenetic analyses (mITT-GT), and on the mITT-GT population further modified to exclude subjects who did not achieve SVR₁₂ for reasons other than virologic failure (mITT-GT-VF).

No data will be imputed for any efficacy or safety analysis except for analyses of SVR endpoints (HCV RNA data). HCV RNA values will be selected for the analyses of all SVR endpoints (e.g., SVR₄, SVR₁₂, and SVR₂₄) based on defined visit windows. A backward imputation method will be used to impute missing responses for SVR analyses.

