8.2 Determination of Sample Size

It is anticipated that approximately a total of 80 HCV infected patients, (~30 GT5-infected subjects and ~50 GT6-infected subjects) will be enrolled in the study. A minimum of 15 GT5 and 30 GT6 subjects will be enrolled and up to approximately 16 subjects with compensated cirrhosis (regardless of GT) will be enrolled. No formal hypothesis is being tested. If the observed SVR_{12} rate in this study is 97% among 30 GT5 subjects and 50 GT6 subjects, then the half-width of 2-sided 95% normal approximation intervals are 0.061 and 0.047 for the GT5 and GT6 subjects, respectively.

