5.1.2 Modified Intention-to-Treat (mITT) Populations

Sensitivity analyses of SVR₁₂ as described in Section 10.5, when applicable, will be performed on the ITT population modified to exclude subjects who do not have HCV GT5 or 6 infection or with multiple/mixed genotypes (final HCV genotype as determined in Section 10.8) (mITT-GT), and on the mITT-GT population further modified to exclude subjects who do not achieve SVR₁₂ for reasons other than virologic failure (mITT-GT-VF).

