10.0 Efficacy Analysis

10.1 General Considerations

General Considerations

All efficacy analyses will be performed on the ITT population, unless otherwise specified. To support the primary analysis, sensitivity analyses will be conducted for it using the mITT-GT and mITT-GT-VF populations.

Missing data will be imputed for analyses of the HCV RNA endpoints of SVR and virologic failure as described in Section 6.3 and for analyses of PROs as described in Section 6.3 and Section 10.9.

Plasma HCV RNA levels will be determined for each sample collected by the central laboratory using the Roche COBAS® AmpliPrep/COBAS® TaqMan® HCV Quantitative Test, v2.0. The lower limit of detection (LLOD) and lower limit of quantification (LLOQ) for this assay (regardless of genotype) are both 15 IU/mL.

HCV RNA results that are detectable but not quantifiable are reported as "< 15 IU/ML HCV RNA DETECTED" and those that are undetectable are reported as "HCV RNA NOT DETECTED" in the database.

The notation "HCV RNA < LLOQ" is used to represent all HCV RNA values < 15 IU/mL, including values reported as "HCV RNA NOT DETECTED" or "< 15 IU/ML HCV RNA DETECTED." HCV RNA \geq LLOQ are all quantifiable values of 15 IU/mL or greater.

Definitions for Efficacy Endpoints

A confirmed quantifiable value during treatment is defined as any two consecutive HCV RNA measurements \geq LLOQ (or 100 IU/mL for **Breakthrough**), either both during treatment or at the final treatment measurement and the next consecutive post-treatment measurement. A confirmed quantifiable post-treatment value is defined as any two consecutive post-treatment HCV RNA measurements \geq LLOQ.

Breakthrough = confirmed HCV RNA \geq 100 IU/mL after HCV RNA < LLOQ during the Treatment Period; or confirmed increase from nadir in HCV RNA (two consecutive HCV RNA measurements > 1 log₁₀ IU/mL above nadir) at any time point during the Treatment Period. A single breakthrough value (\geq 100 IU/mL or > 1 log₁₀ above nadir) followed by lost to follow-up also will be considered a breakthrough (i.e., will not require confirmation).

EOT failure = HCV RNA \geq LLOQ at end of treatment with at least 6 weeks of treatment, where the HCV RNA value must be collected on or after Study Drug Day 36 and study drug duration \geq 36 days.

On-treatment virologic failure = Breakthrough or EOT failure; if a subject meets both definitions of Breakthrough and EOT failure, he or she will be categorized as Breakthrough only.

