SVR₄ = HCV RNA $<$ LLOQ in the SVR₄ window (4 weeks after the last actual dose of study drug) without any confirmed quantifiable (\geq LLOQ) post-treatment value before or during that SVR window.

SVR₁₂ = HCV RNA $<$ LLOQ in the SVR₁₂ window (12 weeks after the last actual dose of study drug) without any confirmed quantifiable (\geq LLOQ) post-treatment value before or during that SVR window.

SVR₂₄ = HCV RNA $<$ LLOQ in the SVR₂₄ window (24 weeks after the last actual dose of study drug) without any confirmed quantifiable (\geq LLOQ) post-treatment value before or during that SVR window.

Relapse₁₂ = confirmed HCV RNA \geq LLOQ between end of treatment and 12 weeks after last actual dose of study drug (up to and including the SVR₁₂ window) for a subject with HCV RNA $<$ LLOQ at Final Treatment Visit who completed treatment, excluding reinfection as described below.

Relapse₂₄ = confirmed HCV RNA \geq LLOQ within the SVR₂₄ window for a subject who achieved SVR₁₂ and has HCV RNA data available in the SVR₂₄ window, excluding reinfection.

Relapse_{overall} = confirmed HCV RNA \geq LLOQ between end of treatment and up to and including the last HCV RNA measurement collected in the Post-Treatment Period for a subject with HCV RNA $<$ LLOQ at Final Treatment Visit who completed treatment, excluding reinfection.

Virologic failure for SVR₁₂ = On-treatment virologic failure or Relapse₁₂.

Only subjects who have at least one post-treatment HCV RNA value will be included in analyses of relapse. For the analysis of relapse, completion of treatment is defined as any subject with study drug duration of 52 days or greater for Arm A, and 77 days or greater for Arm B. If the last available post-treatment value is \geq LLOQ, then the subject will be considered a relapse (i.e., will not require confirmation).

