HCV reinfection is defined as confirmed HCV RNA \geq LLOQ after the end of treatment in a subject who had HCV RNA $<$ LLOQ at Final Treatment Visit, along with the post-treatment detection of a different HCV genotype, subtype, or clade compared with baseline, as determined by phylogenetic analysis of the NS3/4A or NS5A, and/or NS5B gene sequences. Reinfection in the case of the same HCV subtype is defined as a clade switch, as indicated by the lack of clustering between the baseline and post-treatment sequences by phylogenetic analysis. If phylogenetic analysis is not possible due to technical difficulties, HCV reinfection may be determined with a confirmed HCV genotype or subtype switch by the Versant HCV Genotype Inno-LiPA Assay v2.0 or Sanger assay.

Post-treatment relapse is defined as described earlier (**Relapse₁₂**, **Relapse₂₄**, **Relapse_{overall}**), and no genotype, subtype, or clade switch compared with baseline as determined by phylogenetic analysis of the NS3/4A or NS5A, and/or NS5B gene sequences. If phylogenetic analysis is not possible due to technical difficulties, the subject will be defined as having a post-treatment relapse unless an HCV genotype or subgenotype switch is confirmed by the Versant HCV Genotype Inno-LiPA Assay v2.0 or Sanger assay.

Reasons for SVR₁₂ Non-Response

Subjects who do not achieve SVR₁₂ (SVR₁₂ non-responders) will be categorized as having:

1. On-treatment virologic failure (see **On-treatment virologic failure** definition);

2. HCV reinfection (see definition described earlier);
3. Relapse₁₂;
4. Prematurely discontinued study drug with no on-treatment virologic failure (defined as any SVR₁₂ non-responder who prematurely discontinued study drug [study drug duration < 52 days for subjects in Arm A, and < 77 days for subjects in Arm B] and did not meet the **On-treatment virologic failure or HCV reinfection** definitions);
5. Missing follow-up data in the SVR₁₂ window (defined as any subject who completed study drug without data in the SVR₁₂ window after applying the imputation rules and not meeting the definitions of [1], [2], [3], or [4]);
6. Other (defined as any SVR₁₂ non-responder not meeting the definitions of [1] – [5]).

Reasons for SVR₂₄ Non-Response

Subjects who do not achieve SVR₂₄ (SVR₂₄ non-responders) will be categorized as having:

1. On-treatment virologic failure (see **On-treatment virologic failure** definition);
2. HCV reinfection;
3. Relapse₁₂;
4. Relapse₂₄;

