10.7 Additional Efficacy Analyses

As additional analyses, the analyses of SVR₁₂ (as described in Section 10.3) and on-treatment virologic failure and Relapse₁₂ (as described in Section 10.4) in the ITT population and the sensitivity analyses of SVR₁₂ in the mITT-GT and mITT-GT-VF populations (as described in Section 10.5) will be performed for the overall population

across treatment arms and genotypes. For the SVR₁₂ endpoints, two-sided 95% CIs using both the normal approximation to the binomial distribution and the Wilson's score method will be calculated. For the other endpoints, only the two-sided 95% CI using Wilson's score method will be calculated.

The following additional efficacy endpoints will be summarized and analyzed for the ITT population, by GT (GT5 and GT6) across treatment arms and overall:

- The percentage of subjects with HCV RNA < LLOQ at each post-baseline visit in the Treatment Period (using data as observed);
- The percentage of subjects with SVR₄;
- The percentage of subjects with SVR₂₄;
- The percentage of subjects who relapsed after achieving SVR₁₂ (**Relapse₂₄**).
- The percentage of subjects with virologic failure through Post-Treatment Week 12 (i.e., the SVR₁₂ non-responders due to **on-treatment virologic failure** or **Relapse₁₂**)

For each of the above endpoints, a two-sided 95% CI using Wilson's score method will be calculated along with the number and percentage of subjects. Imputations for missing data will be performed as described in Section 6.3 for all the additional endpoints listed above except the first one.

For the overall ITT population and by GT, a summary of the subjects who completed treatment and relapsed (defined as **Relapse_{overall}**) will be prepared displaying the number and percentage of subjects relapsing overall and by the SVR visit window where the first relapse occurred (within the SVR₄, SVR₁₂, SVR₂₄ windows or after SVR₂₄ window), including the subject number and the SVR visit window corresponding to the first occurrence of relapse. A similar summary will be prepared for subjects who prematurely discontinued treatment and relapsed after having HCV RNA < LLOQ at their Final Treatment Visit.

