- Baseline polymorphism: a polymorphism by NGS in a baseline sample ($\geq 2\%$ or $\geq 15\%$ prevalence within a subject's viral population depending on polymorphism frequency threshold utilized) that was not present in the appropriate prototypic reference amino acid sequence for a given DAA target (NS3 or NS5A).
- Variant at signature amino acid position: variant (relative to reference) present in a baseline or a post-baseline sample at a signature amino acid position.

- Post-baseline substitution: an amino acid substitution in a post-baseline time point sample that was not detected at baseline ($< 2\%$) in the subject and is detectable in $\geq 2\%$ of the sequences from the post-baseline sample.
- Enriched variant: a variant present in both the baseline and a post-baseline sample whose prevalence in the post-baseline sample is at least 20 percentage points greater than the prevalence in the baseline sample [(post-baseline % – baseline %) ≥ 20].
- Treatment-emergent substitution by NGS: a post-baseline substitution or an enriched variant.

Analysis 1

The following analyses will be performed for all subjects, separated by HCV genotype/subtype (including total):

- A listing of all subjects with baseline polymorphisms (2% detection threshold) at signature amino acid positions for each DAA target (NS3 and NS5A) in the ITT population. HCV genotype/subtype and treatment outcome (SVR₁₂ or reason for SVR₁₂ non-response) will be displayed for each subject.
- The number and percentage of subjects with baseline polymorphisms at signature amino acid positions at detection thresholds of 2% and 15% for subjects in the ITT population. This table includes prevalence of each baseline polymorphism, and a summary of the number of subjects with polymorphisms in NS3 only, NS5A only, any in NS3 or NS5A, and in both NS3 and NS5A.
- Total number and percentage of subjects in the ITT population with baseline polymorphisms *at a key subset of amino acid positions* in NS3 only, in NS5A only, in NS3 + NS5A, any in NS3, any in NS5A, and any in NS3 or NS5A at 15% detection threshold.

Analysis 2

The impact of baseline polymorphisms on treatment outcome will be assessed for the **mITT-GT-VF** population as follows: for each polymorphism, the SVR₁₂ rate will be calculated for subjects with and without the polymorphism and the two rates will be

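### Documented viral rebound after early stopping is not counted as virologic failure, so the mITT-GT-VF SVR12 rate can only be shifted upward

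*SAP*

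**What the plan says.** Several definitions act together.

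- **Relapse12** (SAP 10.1) requires HCV RNA below LLOQ at the Final Treatment Visit and completed treatment, where "completion of treatment is defined as any subject with study drug duration of 52 days or greater for Arm A" and 77 days for Arm B. Protocol 8.1.2.2 sets the same cut-offs.
- **Virologic failure for SVR12** (SAP 10.1) is on-treatment virologic failure or Relapse12. On-treatment failure is breakthrough or EOT failure. EOT failure is quantifiable RNA "at end of treatment with at least 6 weeks of treatment", which the SAP sets at Day 36 or later.
- **Reason 4 for SVR12 non-response** (SAP 10.1) takes any subject without SVR12 "who prematurely discontinued study drug [study drug duration < 52 days for subjects in Arm A, and < 77 days for subjects in Arm B" who has neither on-treatment virologic failure nor reinfection.
- **mITT-GT-VF** (SAP 5.1.2; Protocol 8.1 agrees) is the mITT-GT set "further modified to exclude subjects who do not achieve SVR₁₂ for reasons other than virologic failure".
- **SVR12** runs from the last actual dose, with no minimum duration of treatment.

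mITT-GT-VF is used for a sensitivity analysis of SVR12 (SAP 10.5) and for the Fisher comparisons in resistance Analyses 2 and 3 (SAP 10.8). Analysis 2 begins "The impact of baseline polymorphisms on treatment outcome will be assessed for the" mITT-GT-VF population. SAP 10.7 adds the percentage with virologic failure through Post-Treatment Week 12, on the ITT population. The same section also says "A similar summary will be prepared for subjects who prematurely discontinued treatment and relapsed" from a suppressed Final Treatment Visit.

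**The concern.** mITT-GT-VF is meant to show SVR12 once failures that are not virologic have been set aside. A measured return of virus after suppression is a virologic outcome, and SAP 10.7 itself describes these subjects as having relapsed. Yet a rebounder with a short course leaves the set, while a subject with the same short course who is cured remains as a success. Among early stoppers, membership then depends on the outcome and works in one direction.

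Relapse24 has no completion condition. An early stopper who rebounds after reaching SVR12 counts as a relapse, while one who rebounds sooner does not.

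Three results are at stake: the mITT-GT-VF SVR12 rate, the virologic-failure percentage in SAP 10.7, and the polymorphism comparisons. In the last of these, the few subjects with rebound carry most of the information.

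**Working it through.** **1. The plan's own figures.** Protocol 8.2 assumes an SVR12 rate of "97% among 30 GT5 subjects and 50 GT6 subjects", and Protocol 8.1 states "All confidence intervals will be two-sided with an alpha level of 0.05". The half-width is 1.96 × √(0.97 × 0.03 / n), which gives 0.061 for n = 30 and 0.047 for n = 50. Both match Protocol 8.2. No figure in either document is attached to the relapse rule.

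**2. Following early stoppers through the definitions.** None of these subjects has breakthrough or reinfection.

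| Early stopper | Coded as | In mITT-GT-VF? |
|---|---|---|
| Suppressed at last visit, reaches SVR12 | Responder | Yes, as a success |
| Suppressed at last visit, then documented rebound by Week 12 | Reason 4 | No |
| Stops before Day 36 still viraemic and stays viraemic | Reason 4 | No |
| Quantifiable at end of treatment, Day 36 or later | EOT failure | Yes, as a failure |

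If four early stoppers are suppressed at their last visit, and two are cured and two rebound, the set keeps 2/2 rather than 2/4.

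**3. Direction.** Let x be the responders and m the members of mITT-GT-VF, and let e rebounders be left out. The reported rate is x/m. With them counted it is x/(m + e), which is never larger.

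**4. Size.** The table assumes e such subjects, no other failures and the planned sample sizes. Intervals are 95% Wilson. When all n subjects respond, the lower limit is n/(n + 1.96²); for example, 29/(29 + 3.84) = 88.3%.

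| Genotype | e | As planned | With rebounders counted |
|---|---|---|---|
| GT5 | 1 | 29/29 = 100% (88.3 to 100) | 29/30 = 96.7% (83.3 to 99.4) |
| GT5 | 2 | 28/28 = 100% (87.9 to 100) | 28/30 = 93.3% (78.7 to 98.2) |
| GT5 | 3 | 27/27 = 100% (87.5 to 100) | 27/30 = 90.0% (74.4 to 96.5) |
| GT6 | 1 | 49/49 = 100% (92.7 to 100) | 49/50 = 98.0% (89.5 to 99.6) |
| GT6 | 2 | 48/48 = 100% (92.6 to 100) | 48/50 = 96.0% (86.5 to 98.9) |
| GT6 | 3 | 47/47 = 100% (92.4 to 100) | 47/50 = 94.0% (83.8 to 97.9) |

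With e = 0 the two columns agree.

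**5. Virologic-failure endpoint (SAP 10.7).** The denominator is ITT, so these subjects stay in it as non-events. With e = 1, GT5 reads 0/30 instead of 1/30 = 3.3% (0.6 to 16.7), and GT6 reads 0/50 instead of 1/50 = 2.0% (0.4 to 10.5).

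**6. Fisher comparisons.** This is an illustration. Carriage of a polymorphism is assumed at 20% or 40%, every rebounder is assumed to be a carrier, and there are no other failures. As planned, no failure is left in the set and p = 1.000. With two rebounders counted in GT5 (n = 30):
- 6 carriers: p = C(6,2)/C(30,2) = 15/435 = 0.034
- 12 carriers: p = 66/435 = 0.152

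In GT6 (n = 50) the values are 45/1225 = 0.037 and 190/1225 = 0.155. With one rebounder, p is 0.200 or 0.400 at either size.

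**The case against.** The rule is pre-specified. The Protocol fixes both the 52/77-day condition (8.1.2.2) and the construction of mITT-GT-VF (8.1), so the SAP does not depart from it there. The cut-offs are also comparable shares of each course: 52/56 = 93% and 77/84 = 92%. This stands, and it is why the pre-specified set should remain.

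The subjects are reported elsewhere. mITT-GT keeps them as failures (SAP 10.5). They also appear in the table and listing of reasons for non-response (10.3), the listing of subjects excluded from mITT-GT-VF (10.5) and the separate summary in 10.7. Their post-treatment samples are sequenced if RNA is at least 1000 IU/mL, and the substitutions are listed (10.8). A reader might infer that the plan conceals these relapses; it does not. None of that reporting, however, feeds the three affected analyses.

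A reader might also see a contradiction between Day 36 for EOT failure and Day 77 for Arm B relapse. The documents do not support that: one rule concerns viraemia at the end of treatment, the other viral return after a course treated as complete.

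Finally, adding under-treated subjects to the polymorphism comparisons mixes short exposure with viral genetics. That is a fair reason to show both versions. It is not a reason to show only the one that keeps cured early stoppers.

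**Conclusion.** The point holds for mITT-GT-VF, for the event count of the SAP 10.7 virologic-failure endpoint and for resistance Analyses 2 and 3. Each subject with documented rebound after early stopping moves the mITT-GT-VF SVR12 rate up by about 3.3 points in GT5 and 2.0 points in GT6 at the planned sizes, and the shift cannot go the other way. At the assumed 97%, about one GT5 failure is expected (30 × 0.03 = 0.9), so one such subject could account for all of it.

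How often this would occur is unknown. A reader might infer a rate from the 2 of 276 (0.7%) adverse-event discontinuations given in Protocol Appendix E. Those come from earlier 12-week arms with mixed doses, some with ribavirin. Protocol 3.0 also reports no discontinuations among 82 cirrhotic subjects. Neither figure gives the chance of stopping before 52 or 77 days here, or of rebound afterwards. The counts of one to three above are assumptions, and zero is possible.

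A reader might further infer that the main efficacy result is biased. It is not: ITT SVR12 counts these subjects as failures, and Relapse12 among completers is unchanged. Nor does either document call mITT-GT-VF the principal sensitivity analysis; it is one of several. This is a worthwhile correction to supporting analyses.

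**What to change.** In SAP 10.1, add a flag for documented virologic failure regardless of treatment duration. It is met by any of:
- on-treatment virologic failure;
- Relapse12;
- in any early discontinuer, confirmed post-treatment HCV RNA at or above LLOQ through the SVR12 window, or a last available post-treatment value at or above LLOQ, excluding reinfection.

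The third item should apply whether or not the subject was suppressed at the Final Treatment Visit. Otherwise someone who stops before Day 36 still viraemic, without breakthrough, would still be dropped.

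Report mITT-GT-VF SVR12 (5.1.2, 10.5), the virologic-failure percentage (10.7) and resistance Analyses 2 and 3 (10.8) with this flag, next to the pre-specified versions. Keep Relapse12 among completers as the secondary endpoint.

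The cost is SAP wording, one derived variable and a few extra tables, with no new data. The mITT-GT-VF rate may look slightly less favourable, and the added polymorphism comparisons will include some under-treated subjects, which a footnote should state.

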8.1.2.2 Secondary Efficacy Endpoints

The secondary efficacy endpoints within each genotype (GT5 and GT6 subjects) separately, across treatment arms are:

- The percentage of subjects with HCV on-treatment virologic failure;
- The percentage of subjects with post-treatment HCV virologic relapse. Subjects with reinfection based on HCV NGS will be summarized separately from relapse.

The secondary endpoints of HCV on-treatment virologic failure and post-treatment HCV virologic relapse will be analyzed within each genotype (GT5 and GT6 subjects) separately, across the treatment arms.

For the analysis of post-treatment HCV virologic relapse, completion of treatment is defined as any subject with study drug duration of 52 days and 77 days or greater for subjects allocated to treatment durations of 8 weeks and 12 weeks, respectively.

For on-treatment virologic failure and post-treatment relapse, the number and percentage of subjects will be summarized along with a two-sided 95% confidence interval using Wilson's score method.

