5. Prematurely discontinued study drug with no on-treatment virologic failure (defined as any SVR₂₄ non-responder who prematurely discontinued study drug [study drug duration < 52 days for subjects in Arm A, and < 77 days for subjects in Arm B] and did not meet the **On-treatment virologic failure, HCV reinfection, Relapse₁₂, or Relapse₂₄** definitions);

6. Missing follow-up data in the SVR₂₄ window (defined as any subject who completed study drug without data in the SVR₂₄ window after applying the imputation rules and not meeting the definitions of [1], [2], [3], [4], or [5]);
7. Other (defined as any SVR₂₄ non-responder not meeting the definitions of [1] – [6]).

For the reasons for SVR₁₂ and SVR₂₄ nonresponse defined above, subjects are only to be counted in one category in the order shown above. Specifically, subjects who were SVR₁₂ or SVR₂₄ nonresponders meeting the definition of HCV reinfection will be counted in the reinfection category regardless of whether they meet the definition of prematurely discontinued study drug, Relapse₁₂ or Relapse₂₄.

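### A genotype, subtype or clade switch seen only at the last available visit cannot be classed as HCV reinfection, because SAP 10.1 waives confirmation for relapse but not for reinfection

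*SAP*

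**What the plan says.** All the rules are in SAP 10.1 unless stated.

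- **Confirmation.** "A confirmed quantifiable post-treatment value is defined as any two consecutive post-treatment HCV RNA measurements" at or above LLOQ.
- **Relapse, RNA rule.** Relapse12 needs a confirmed value in a subject below LLOQ at the Final Treatment Visit "who completed treatment, excluding reinfection as described below". A later sentence relaxes this: if the last available post-treatment value is at or above LLOQ, "then the subject will be considered a relapse (i.e., will not require confirmation").
- **Relapse, sequence rule.** Post-treatment relapse is the earlier definition "and no genotype, subtype, or clade switch compared with baseline as determined by phylogenetic analysis".
- **Reinfection.** "HCV reinfection is defined as confirmed HCV RNA" at or above LLOQ after treatment, in a subject below LLOQ at the Final Treatment Visit, plus a different genotype, subtype or clade. The Inno-LiPA or Sanger fallback replaces the phylogenetic evidence only, not the RNA confirmation.
- **Precedence.** Those "meeting the definition of HCV reinfection will be counted in the reinfection category regardless of whether they meet the definition of prematurely discontinued study drug" or relapse. This helps only subjects who already meet the reinfection definition.
- **Protocol 8.1.2.2.** "Subjects with reinfection based on HCV NGS will be summarized separately from relapse". No confirmation condition is stated there.

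**The concern.** Relapse and reinfection compete to explain the same observation, a quantifiable value after a negative end of treatment, and sequence data are meant to separate them. Here they are held to different RNA standards. When the only positive value is the last one available, relapse is open and reinfection is closed, even if sequencing shows a different virus.

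The visit schedule makes this reachable. Post-treatment visits are at Weeks 4, 12 and 24 (SAP 4.2; Protocol Appendix D), so no scheduled visit can confirm a first positive at Week 24. A first positive at Week 12 may still be the last value at the primary lock, and SAP 4.4 says SVR12 results are not updated afterwards. The confirmatory testing in Protocol 5.4.1.1 concerns failure on study drug.

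At stake are the reason-for-non-response tables and the separate reinfection summary that the protocol asks for. On one reading of the waiver, the relapse counts are affected too.

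**Working it through.** The plan gives no figure on this point, so the check applies the rules to cases and then sizes one misplaced subject.

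**Step 1. Classification.** Take a subject below LLOQ at the Final Treatment Visit, with a switch shown by sequencing and one post-treatment value at or above LLOQ, which is the last available. Reading A applies the no-switch condition together with the waiver. Reading B lets the waiver stand alone.

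| Case | Reading A | Reading B |
|---|---|---|
| Completer, value in SVR12 window | Other | Relapse12 |
| Completer, last value before SVR12 window | Missing follow-up data | Relapse12 |
| Stopped study drug early (SVR12 reasons) | Prematurely discontinued | Prematurely discontinued |
| Completer, SVR12 responder, first positive at Week 24 (SVR24 reasons) | Other | Relapse24 |

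No row gives reinfection. With two consecutive positives and the same switch, these subjects are reinfections under both readings, so the missing last-value rule is the sole cause. The early-stopper row is limited to the SVR12 table: Relapse24 carries no completion condition, so an early stopper who reached SVR12 could still be Relapse24 under reading B.

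**Step 2. Which outputs each case can touch.**

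- First positive at Week 24 after negative Weeks 4 and 12: the subject is an SVR12 responder. Only Relapse24, Relapse_overall and the SVR24 reasons are in play.
- First positive in the SVR12 window (days 57 to 126, SAP Table 2) and still the last value at the primary lock: the SVR12 reasons are affected. Relapse12, virologic failure and mITT-GT-VF are affected under reading B only. Under reading A the subject leaves mITT-GT-VF just as a reinfection would (SAP 5.1.2).
- ITT SVR12: the subject is a non-responder under every label, so it is unchanged.

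**Step 3. Size under reading B.** Inputs: n = 30 (GT5) and n = 50 (GT6) from Protocol 8.2; two-sided 95% Wilson intervals from SAP 10.4; one such subject and no other failures, with all planned subjects in the relapse denominator (assumptions).

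Wilson limits, with p = x/n and z = 1.96:

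[p + z²/(2n) ± z·√(p(1−p)/n + z²/(4n²))] / (1 + z²/n)

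For x = 0 the upper limit reduces to z²/(n + z²): 3.84/53.84 = 7.1% (GT6) and 3.84/33.84 = 11.4% (GT5).

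For 1/50: centre (0.0200 + 0.0384)/1.0768 = 0.0542; half-width 1.96 × √(0.000392 + 0.000384)/1.0768 = 0.0507; interval 0.4 to 10.5%.

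| | Counted as relapse | Counted as reinfection |
|---|---|---|
| GT6 Relapse12 | 1/50 = 2.0% (0.4 to 10.5%) | 0/50 = 0% (0 to 7.1%) |
| GT5 Relapse12 | 1/30 = 3.3% (0.6 to 16.7%) | 0/30 = 0% (0 to 11.4%) |
| GT6 mITT-GT-VF SVR12 | 49/50 = 98.0% (89.5 to 99.6%) | 49/49 = 100% (92.7 to 100%) |
| GT5 mITT-GT-VF SVR12 | 29/30 = 96.7% (83.3 to 99.4%) | 29/29 = 100% (88.3 to 100%) |

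Under reading A the right-hand column holds, and only the reason label is wrong.

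**The case against.** A reader might infer that the SAP contradicts itself and charges new infections to the drug as relapse. The documents do not support that as the natural reading. The no-switch condition is joined to the relapse definitions by "and", so the conditions are cumulative. The waiver explains itself as removing confirmation, not the other criteria. Read as an override, it would also turn an on-treatment failure with a positive last value into a relapse, against the requirement of a negative Final Treatment Visit. The fallback for failed phylogenetics points the same way, since a switch confirmed by another assay defeats relapse. This part of the objection stands, and it removes Relapse12, virologic failure and mITT-GT-VF from the expected consequences.

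The case is also narrow. It needs a new infection, no repeat sample, and a sample that can be typed; SAP 10.8 sequences at 1000 IU/mL or more. An unscheduled repeat could supply confirmation. For the SVR12 case there must also be no Week 24 value at the lock, and under SAP 4.4 early enrollees may already have one (Protocol 8.1 instead puts data after Week 12 into a later database version). By-subject listings of non-responders would show the case. All this stands and limits the priority.

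A last argument is that a stricter standard for reinfection is prudent, because that label takes a subject out of virologic failure. This does not stand. Under the cumulative reading a shown switch has already taken the subject out of relapse, so demanding confirmation protects nothing and only mislabels the reason.

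**Conclusion.** The gap is real and minor. A completer with a demonstrated switch seen only at the last available visit cannot be reported as a reinfection, although Protocol 8.1.2.2 asks for reinfection to be shown separately. On the more natural reading the damage is one subject in the wrong row (Other or missing follow-up data) and absent from the reinfection summary. Only if a programmer applies the waiver alone does the subject become a relapse, with the one-subject shifts shown above. Those shifts apply to a first positive in the SVR12 window, not to one at Week 24.

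The primary ITT SVR12 result is unaffected. The one-subject count is an assumption: the documents give no reinfection incidence, and it may be zero.

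**What to change.** Make two wording changes in SAP 10.1 before the primary lock.

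1. In the reinfection definition, replace the RNA requirement with: *confirmed HCV RNA ≥ LLOQ, or HCV RNA ≥ LLOQ at the last available post-treatment value, together with a genotype, subtype or clade switch*. Keep the existing requirement for a value below LLOQ at the Final Treatment Visit.
2. To the relapse waiver, add: *provided all other relapse criteria are met and the reinfection criteria are not met*.

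The cost is two sentences and one derivation line, with no new samples or visits. The small downside is that a reinfection label may then rest on one sequenced sample. Relapse may already rest on one value, and here there is sequence evidence as well.
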